6.4. Post-treatment Assessments

6.4.1. Early Study Drug Discontinuation (ESDD) Visit

If a subject discontinues study drug prior to the Week 48 visit, the subject will be asked to return to the clinic within 72 hours of stopping study drug for the ESDD visit. The subject will be asked to continue attending the scheduled study visits through Week 48.

At the ESDD Visit, any evaluations showing abnormal results indicating that there is a possible or probable causal relationship with the study drug, will be repeated weekly (or as often as deemed prudent by the Investigator) until the abnormality is resolved, returns to baseline, or is otherwise explained.

The following evaluations are to be completed at the Early Study Drug Discontinuation Visit:

- Review of AEs and changes in concomitant medications
- Complete physical examination (urogenital/anorectal exams will be performed at the discretion of the Investigator)
- 12-lead ECG performed supine
- Vital signs (blood pressure, pulse, respiration rate, and temperature), including weight
- Urine collection for the following laboratory procedures:
 - Urinalysis and urine chemistry
 - Urine pregnancy test (females of childbearing potential only); positive urine pregnancy tests will be confirmed with a serum test.
 - Urine sample storage for possible additional clinical testing
- Blood sample collection for the following laboratory analyses:
 - Chemistry profile: alkaline phosphatase, AST, ALT, total bilirubin, direct and indirect bilirubin, total protein, albumin, bicarbonate, BUN, calcium, chloride, creatinine, glucose, potassium and sodium
 - Estimated GFR, according to the Cockcroft-Gault formula for creatinine clearance
 - Hematology profile: CBC with differential and platelet count
 - Plasma HIV-1 RNA
 - CD4+ cell count
 - Plasma sample storage for safety and virology testing
 - **CCI**

- Questionnaire: Subject is to read questionnaire by her/himself and write/mark answers directly onto questionnaire.
 - Visual Analog Scale (VAS)
 - HIV-TSQc
- HIV-1 genotype/phenotype resistance testing for subjects with unconfirmed virologic rebound with HIV-1 RNA value ≥ 50 copies/mL
- Questionnaire: Subject is to read questionnaire by her/himself and write/mark answers directly onto questionnaire.
 - HIV Treatment Satisfaction Questionnaire Change (HIV-TSQc)
- Study drug accountability

6.4.2. 30-Day Follow-up Visit

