6.5. Assessments for Premature Discontinuation from Study

If a subject discontinues study dosing (for example, as a result of an AE), every attempt should be made to keep the subject in the study (see Section 6.6, Criteria for Discontinuation of Study Treatment) and continue to perform the required study-related follow-up and procedures. If this is not possible or acceptable to the subject or Investigator, the subject may be withdrawn from the study.

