6.8.2. Resistance Analysis at Subjects Last Visit

Subjects with HIV-1 RNA $<$ 50 copies/mL could experience unconfirmed blips of HIV-1 RNA \geq 50 copies/mL at their last study visit. Such subjects will be analyzed for resistance if the unconfirmed rebound happens at Week 48 or at the last visit while taking study drug (or within 72 hours of discontinuation of study drug).

Figure 6-1. Management of Virologic Failure

- a If virologic rebound is not confirmed, the subject will remain on the study drug.
- b If virologic rebound is confirmed, and the HIV-1 RNA is ≥ 50 copies/mL, the HIV-1 genotype and phenotype (reverse transcriptase, protease and integrase resistance) will be analyzed.
- c Based on the results of the genotype/phenotype assays, the subject will remain or discontinue study drug. If genotyping/phenotyping assay fails, a new ARV regimen may be configured at the discretion of the Investigator in consultation with the Medical Monitor.
- d If no resistance detected, HIV-1 RNA will be repeated (2-4 weeks later). Investigator reviews study drug continuation/discontinuation options and discusses with Medical Monitor prior to discontinuation.
- e A new ARV regimen will be configured, at the Investigator's discretion, and the subject will remain in the study.

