8.4. Efficacy Analysis

8.4.1. Primary Analysis

The primary endpoint of pure virologic response (PVR) with HIV-1 RNA < 50 copies/mL at Week 12 will be computed.

The following criteria are considered for classifying subjects as a pure virologic responder at Week 12:

- Subject remains on study treatment
- No confirmed rebound as defined by:
 - HIV-1 RNA \geq 50 copies/mL on 2 consecutive visits;
 - HIV RNA \geq 50 copies/mL during study followed by premature discontinuation of study

Note: For confirmation of viral rebound, the first HIV-1 RNA must occur on or before the upper limit of the Week 12 analysis window, the confirming event (i.e., the second of the consecutive HIV-1 RNAs or premature study discontinuation) can occur after the upper limit of the Week 12 analysis window.

Subjects who meet the above criteria are pure virologic responders at Week 12; otherwise subjects are pure virologic failures (PVF) at Week 12. The 95% CI will be computed using normal approximation to the binomial proportions of PVR

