##### **3.1.2. Full Analysis Set**

The Full Analysis Set (FAS) will include all the subjects who were enrolled and received at least one dose of study drug. For the FAS, all efficacy data will be included, unless specified otherwise. The FAS is the primary analysis set for the efficacy analyses.

Subjects meeting the following criteria will be excluded from the FAS:

- Subjects who took Stribild or Descovy as part of the baseline antiretroviral (ARV) regimen and thus violated the inclusion criterion.

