## 6. EFFICACY ANALYSES

### 6.1. Primary Efficacy Endpoint

#### 6.1.1. Definition of Primary Efficacy Endpoint

The primary efficacy endpoint is the proportion of subjects with HIV-1 RNA < 50 copies/mL at Week 12 as defined by PVR.

##### 6.1.1.1. Definition of Pure Virologic Response at Week 12

The following criterion is considered for classifying subjects as a pure virologic responder at Week 12:

- No confirmed rebound (ie, no instances of either HIV-1 RNA  $\geq$  50 copies/mL on 2 consecutive visits or last available HIV-1 RNA  $\geq$  50 copies/mL followed by premature discontinuation of study) by the upper limit of the Week 12 analysis window.

**Note:** For confirmation of virologic rebound, the first HIV-1 RNA datum must occur on or before the upper limit of the Week 12 analysis window. The confirming event (ie, the second of the 2 consecutive HIV-1 RNA values or premature study discontinuation) can occur after the upper limit of the Week 12 analysis window.

Subjects who meet the above criterion are PVRs at Week 12; otherwise subjects are pure virologic failures (PVFs) at Week 12.

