##### **6.2.2.2. Time to Pure Virologic Failure Analysis**

For subjects who do not experience a confirmed rebound (ie, HIV-1 RNA  $\geq$  50 copies/mL on 2 consecutive visits or the last available HIV-1 RNA  $\geq$  50 copies/mL followed by premature discontinuation of study), subjects will be censored at the last HIV-1 RNA collection date. For subjects who experience confirmed rebound, the time to PVF will be defined as the earlier time of 2 consecutive HIV-1 RNA  $\geq$  50 copies/mL or the last available HIV-1 RNA  $\geq$  50 copies/mL followed by premature discontinuation of study.

Time to PVF will be analyzed using the KM method by Part 1 and Part 2 using the FAS.

Lastly, subjects who failed according to snapshot algorithm, pure virologic failure analysis algorithms, or had premature study drug discontinuation by Week 48 will be listed.

6.2.2.3. Analysis of proportion of subjects with HIV-1 RNA < 50 copies/mL at Weeks 12, 24, and 48 as determined by the US FDA-defined snapshot algorithm

The analysis windows for Weeks 12, 24, and 48 are defined in [Table 3-1](#). All HIV-1 RNA data collected on-treatment (eg, data collected up to 1 day after the last dose date of study drug) will be used in the US FDA-defined snapshot algorithm. Virologic outcome will be defined as the following categories:

- **HIV-1 RNA < 50 copies/mL:** this includes subjects who have the last available on-treatment HIV-1 RNA < 50 copies/mL in the analysis window
- **HIV-1 RNA ≥ 50 copies/mL:** this includes subjects:
  - a. Who have the last available on-treatment HIV-1 RNA ≥ 50 copies/mL in the analysis window, or
  - b. Who do not have on-treatment HIV-1 RNA data in the analysis window and
    - 1) Who discontinue study drug prior to or in the analysis window due to lack of efficacy (note: Lack of efficacy is defined as having the check-box for Lack of efficacy marked on the Study Drug Completion eCRF), or
    - 2) Who discontinue study drug prior to or in the analysis window due to AE or death and have the last available on-treatment HIV-1 RNA ≥ 50 copies/mL
    - 3) Who discontinue study drug prior to or in the analysis window due to reasons other than AE, death, or lack of efficacy and have the last available on-treatment HIV-1 RNA ≥ 50 copies/mL
- **No Virologic Data (in the Window):** this includes subjects who do not have on-treatment HIV-1 RNA data in the analysis window because of the following:

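### Rebound is confirmed by leaving the study, not by stopping study drug, and off-drug samples count, so pure virologic response misclassifies a narrow group who stop E/C/F/TAF

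*SAP*

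**What the plan says.** SAP 6.1.1.1 has one criterion for a Week 12 responder: no confirmed rebound. The first elevated value (HIV-1 RNA of 50 copies/mL or more) must fall on or before the end of the Week 12 window. The event that confirms it may come later, and is "the second of the 2 consecutive HIV-1 RNA values or premature study discontinuation". On the second limb the elevated value must be the last one available, "followed by premature discontinuation of study) by the upper limit of the Week 12 analysis window". SAP 6.1.1.2, 6.1.1.3 and 6.2.2.2 carry the same two limbs into Week 48, the joint table of failure and drug discontinuation, and the time-to-failure analysis.

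No sentence limits PVR to samples taken on study drug. SAP 3.1.2 says "For the FAS, all efficacy data will be included, unless specified otherwise". SAP 6.1.1.2 has a category for subjects who stop drug first and meet the failure criteria afterwards. Time to failure is censored at the last HIV-1 RNA collection, on drug or not. For the snapshot outcome, by contrast, SAP 6.2.2.3 sets a limit: "All HIV-1 RNA data collected on-treatment (eg, data collected up to 1 day after the last dose date of study drug) will be used". The CD4 analyses have the same limit.

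Protocol 8.4.1 gives two criteria for a responder. The first is "Subject remains on study treatment"; the second is absence of confirmed rebound. The SAP keeps only the second. SAP 6.3 reports one change from the protocol's efficacy analyses, the added exact confidence interval.

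Stopping drug is not leaving the study. Protocol 6.4.1 says of a subject who stops early: "The subject will be asked to continue attending the scheduled study visits through Week 48". Protocol 6.5 adds that "every attempt should be made to keep the subject in the study".

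**The concern.** The objectives ask whether E/C/F/TAF maintains suppression at Week 12 and durably at Weeks 24 and 48. Under the SAP rule the sample that settles an on-drug elevation may be taken on another regimen. That regimen's effect can then cancel the elevation, because stopping study drug does not itself complete the rebound. The rule can also err the other way: a subject suppressed throughout E/C/F/TAF whose virus rises only after stopping can be charged to E/C/F/TAF as a failure.

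The same definitions set event and censoring times for time to failure and fill the cells of the joint table. With Part 1 PVR reported as 100% and the study cut to 64 subjects (SAP 1.3), the result rests on very few failures.

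**Working it through.** **The plan's own figures.** The half-width of the 95% CI is 1.96 × √(p(1 − p)/n).
- p = 0.90, n = 100: 1.96 × √(0.09/100) = 0.0588, stated as 5.9%.
- p = 0.95, n = 64: 1.96 × √(0.0475/64) = 0.0534, stated as 5.3%.

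Both reproduce, and neither depends on how rebound is confirmed.

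**Classification of hypothetical histories.** The Week 12 window ends on Day 98 (SAP Table 3-1). High means 50 copies/mL or more, low means below 50; R is responder and F is failure at Week 12. Three rules are compared: the SAP rule; the protocol rule (SAP rule plus still on study treatment at Week 12); and an on-treatment rule in which stopping study drug also completes rebound and the Early Study Drug Discontinuation (ESDD) sample counts as on-treatment.

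| History | SAP | Protocol | On-treatment |
|---|---|---|---|
| 1. High Day 56 on drug, stops, ESDD sample missed, low Day 84 on another regimen, stays | R | F | F |
| 2. Low on drug, stops before Week 12, first high at ESDD, low at next sample on another regimen, stays | R | F | F |
| 3. High Day 84 on drug, stops after Day 98, no sample until low Day 112 on another regimen | R | R | F |
| 4. High Days 56 and 77 on drug, then changes regimen | F | F | F |
| 5. High Day 56, high at ESDD Day 60, then changes regimen | F | F | F |
| 6. High Day 56 on drug, stops, next off-drug value high | F | F | F |
| 7. Low on drug, stops Day 40, high off drug Days 56 and 84 | F | F | R |
| 8. Low on drug, stops Day 40, high at 30-Day Follow-up (about Day 40 + 30 = 70), leaves study | F | F | R |
| 9. High Day 56, stays on drug, low Day 84 | R | R | R |

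Histories 1 to 3 are wrongly favourable under the SAP. Histories 7 and 8 charge off-drug values to E/C/F/TAF. Histories 4 to 6 fail under every rule.

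History 3 shows that restoring the protocol criterion at Week 12 alone does not close the gap. The retest is due 14 to 28 days after Day 84, on Days 98 to 112, so the stop can follow the window. Carried to Weeks 24 and 48 through the similar definition in Protocol 8.4.2, the criterion would make that subject a failure there. It would equally fail a suppressed subject who stops drug for any reason.

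**Size.** The size of the Full Analysis Set is not given. SAP 1.3 gives a study size of 64, and SAP 3.1.2 excludes some subjects. Assuming 64, one subject is 1/64 = 1.6 points. Exact (Clopper-Pearson) 95% intervals:
- 64/64 = 100%: 94.4 to 100
- 63/64 = 98.4%: 91.6 to 100.0
- 62/64 = 96.9%: 89.2 to 99.6

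Assuming 60, one subject is 1/60 = 1.7 points: 60/60 gives 94.0 to 100 and 59/60 gives 91.1 to 100.0.

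**The case against.** A reader might infer that anyone viraemic on E/C/F/TAF who changes regimen and stays in follow-up is scored a responder. The documents do not support that: two consecutive elevated values are failure whatever happens next. A reader might also take footnote e of protocol Figure 6-1, where a new regimen is configured "and the subject will remain in the study", as the route into the gap. It appears to describe the end of a pathway that runs through retest, confirmation and resistance testing, so those subjects have already failed. Footnote a keeps a subject with unconfirmed rebound on study drug.

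The ESDD visit narrows the gap further. A subject who stops early is asked back within 72 hours and HIV-1 RNA is measured. If an earlier elevation is still present, the subject fails; if the value is low that soon after the last dose, the elevation was probably a blip. Case (i) therefore needs either a first elevation at ESDD or a missed ESDD sample. Protocol 6.8.2 does foresee the first of these, since it asks for resistance analysis of an unconfirmed rebound at the last visit on drug or within 72 hours of stopping.

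The study-discontinuation limb is the protocol's own wording in 8.4.1, and the joint table reports discontinuers separately, so preferring an on-treatment rule is partly a choice of estimand. That stands. It does not excuse dropping the protocol's treatment criterion without declaring it.

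Other outputs also help. Snapshot at Week 12 would score histories 1 and 3 as 50 or above, and premature drug discontinuations by Week 48 are listed. One limit remains: an ESDD value taken more than 1 day after the last dose lies outside the snapshot's on-treatment data, so history 2 may be visible only in the listing. None of this changes the primary PVR figure.

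**Conclusion.** The point holds in a limited form. The SAP rule can score as a responder (i) a subject whose last on-drug result is a single unconfirmed elevation, who stops drug, stays in follow-up and is next measured low on another regimen. It can score as a failure (ii) a subject whose elevated values arise only after stopping. That off-drug samples count is inferred from SAP 3.1.2, the drug-stop-then-failure category and the censoring rule; it is not stated outright for PVR. The undeclared loss of the protocol's treatment criterion is plain on the text.

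The effect is 1.6 points per subject if the Full Analysis Set is 64. The documents do not say how many subjects, if any, are affected. No hypothesis is tested (SAP 6.1.2). The only benchmark is the 80% PVR in the protocol synopsis, and two such subjects (62/64, lower limit 89.2%) would leave the interval above it. A claim that the trial's conclusion is at risk would go beyond the documents. This should be fixed, but it is not a must-fix.

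**What to change.** In SAP 6.1.1.1, 6.1.1.2, 6.1.1.3 and 6.2.2.2:
- Define rebound as either two consecutive on-treatment values of 50 copies/mL or more, or a last on-treatment value of 50 or more followed by premature discontinuation of study drug or study.
- For this endpoint, treat the ESDD sample (within 72 hours of the last dose) as on-treatment. The last-dose-plus-1-day cut in Appendix 5 item 25 would discard a valid ESDD result and could turn a cleared blip into a failure.
- Censor time to failure at the last on-treatment value, and list off-drug values separately.
- Keep the present all-data rule as a sensitivity analysis.
- State how a first elevation at Week 48 is scored. Study drug then stops by design, and the 30-Day Follow-up (about Day 336 + 30 = 366) still lies inside the Week 48 window of Days 295 to 378.

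Reconcile with Protocol 8.4.1 by restoring the still-on-treatment criterion or declaring its removal, and record every departure in SAP 6.3.

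The cost is SAP wording, one data filter and one sensitivity table. The reported PVR may fall slightly if case (i) occurred; resolving case (ii) moves it the other way.

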8.1.2. Primary Endpoint

The primary endpoint is the proportion of subjects with HIV-1 RNA <50 copies/mL at Week 12 as defined by pure virologic response.

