### **3.5. Missing Data and Outliers**

#### **3.5.1. Missing Data**

A missing data point for a given study visit may be due to any of the following reasons:

- A visit occurred in the window but data were not collected or were unusable
- A visit did not occur in the window
- A subject permanently discontinued from the study before reaching the window.

In general, values for missing data will not be imputed, unless otherwise specified.

For missing last dosing date of study drug, imputation rules are described in Section 3.5.1 and the SAP [Appendix 5](#). The handling of missing or incomplete dates for AE onset is described in Section 7.1.6.2, and for concomitant medications in Section 7.5.2 as well as the SAP [Appendix 5](#).

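### The Week 12 primary rule counts a treated subject with no HIV-1 RNA result after Day 1 as a responder

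*SAP*

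**What the plan says.** SAP 6.1.1 names the endpoint: "The primary efficacy endpoint is the proportion of subjects with HIV-1 RNA < 50 copies/mL at Week 12 as defined by PVR". SAP 6.1.1.1 then gives a single condition, introduced by "The following criterion is considered for classifying subjects as a pure virologic responder at Week 12", namely no confirmed rebound. Rebound is either two consecutive values of 50 copies/mL or more, or a last available value of 50 or more before early study withdrawal. The section closes: "Subjects who meet the above criterion are PVRs at Week 12; otherwise subjects are pure virologic failures (PVFs) at Week 12". There is no category for missing data.

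The denominator is set in SAP 3.1.2: "The Full Analysis Set (FAS) will include all the subjects who were enrolled and received at least one dose of study drug". Its one exclusion concerns baseline regimens, not absent virology. Table 3-1 sets the Week 12 HIV-1 RNA window at Days 71 to 98, but the PVR rule does not require a value inside it. SAP 3.5.1 gives the general position on missing data: "In general, values for missing data will not be imputed, unless otherwise specified".

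Protocol 8.4.1 lists a further responder condition, "Subject remains on study treatment". The SAP omits it, and SAP 6.3 reports only the confidence interval method as a change from the protocol.

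**The concern.** The endpoint's name describes a measured state at Week 12. The rule describes the absence of an observed event. The two part company for a subject who was never sampled after Day 1: nothing can be observed, so nothing can be confirmed, and the subject enters the numerator.

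Any such effect raises PVR relative to counting the subject as a non-responder; it cannot lower it. It matters here because SAP 1.3 expects PVR of 95% or higher in 64 subjects, so the result rests on zero to about three failures. PVR also carries decisions: the synopsis calls a value below 80% unacceptable at the interim review, and SAP 1.3 used the Part 1 PVR of 100% to reduce the sample size.

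**Working it through.** **The plan's own figures.** SAP 1.3 gives normal-approximation half-widths, 1.96 × √(p(1 − p)/n).
- p = 0.90, n = 100: 5.88%, stated as 5.9%.
- p = 0.95, n = 64: 5.34%, stated as 5.3%.

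Both reproduce. They neither support nor refute the point, which concerns the definition.

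**Tracing one subject.** Take a subject who is dosed and has no HIV-1 RNA after Day 1.
1. Full Analysis Set: included, since one dose is enough.
2. Two consecutive values of 50 or more after Day 1: impossible without samples.
3. Last available value of 50 or more, then study withdrawal: possible only if the Day 1 value counts. SAP 6.1.1.1 does not say whether it does. SAP 5.2 plans a baseline category of 50 or more, so the case is conceivable.
4. Otherwise: responder at Week 12. SAP 6.1.1.2 defines Week 48 similarly, and Protocol 8.4.2 extends a similar definition to Weeks 24 and 48.

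**The same subject elsewhere in the SAP.** The snapshot (6.2.2.3) does not count the subject as below 50. Missing = Failure (6.2.2.5) counts the subject as 50 or more. Time to failure (6.2.2.2) censors at the last HIV-1 RNA date, so the subject adds no follow-up after Day 1. Only the primary proportion records a success.

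**Size.** The documents give no count of such subjects, so k is an assumption. Each is worth 1/64 = 1.56 points against scoring as a failure. Exact two-sided 95% limits are Clopper-Pearson. The lower limit is the 2.5% quantile of Beta(x, n − x + 1), which for x = n reduces to 0.025^(1/n); for 64/64 that is 0.025^(1/64) = 94.4%.

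With no observed rebound, the current rule gives 64/64, lower limit 94.4%, for every k:

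| k | Scored as failures (95% CI) | Excluded: estimate, lower limit |
|---|---|---|
| 0 | 64/64 = 100% (94.4–100) | 100%, 94.4% |
| 1 | 63/64 = 98.4% (91.6–99.96) | 100%, 94.3% |
| 2 | 62/64 = 96.9% (89.2–99.6) | 100%, 94.2% |
| 3 | 61/64 = 95.3% (86.9–99.0) | 100%, 94.1% |
| 5 | 59/64 = 92.2% (82.7–97.4) | 100%, 93.9% |

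If three subjects do rebound, the current rule gives 61/64 = 95.3%, lower limit 86.9%. Scoring one or two no-data subjects as failures lowers that limit to 84.8% (60/64) or 82.7% (59/64). Excluding them gives 86.7% (60/63) or 86.5% (59/62).

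**The case against.** **Other planned analyses already show these subjects.** This stands in large part. At Week 12 the snapshot has a no-data category and Missing = Failure prints a missing row, both with exact intervals. Neither alters the primary figure. SAP 6.2.2.5 also summarises Missing = Failure only through Week 12, although SAP 6.2.1 names Weeks 24 and 48 for it. The one sensitivity analysis attached to the primary endpoint (SAP 6.1.4.1) concerns baseline regimens, not missing data.

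**The case is unlikely.** Bottles hold 30 tablets, and dispensing at Weeks 4, 8 and 12 falls at the visits where HIV-1 RNA is drawn. Staying on drug to the end of the window with no result would in practice need several attended visits without a usable sample. The realistic case is an early dropout, whom the protocol's on-treatment condition would fail. A reader might infer that restoring that condition would achieve little; on the protocol's procedures it would remove most of the problem, leaving only the subject on drug without samples.

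**There is no conflict with the missing-data rule.** A reader might take the rule as contradicting SAP 3.5.1. It does not literally do so: no value is imputed, that section speaks only in general terms, and Protocol 8.1.2 makes the endpoint hold "as defined by pure virologic response". The effect equals missing = success, but the documents show an unstated default rather than a contradiction.

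**The size depends on the penalty.** This stands. The fall to 91.6% or 89.2% comes from scoring no-data subjects as failures; exclusion barely moves the limit. No hypothesis is tested (SAP 6.1.2), and even k = 5 with no rebounds leaves the lower limit at 82.7%, above the 80% interim benchmark.

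**Conclusion.** The point holds as one about the definition. As written, SAP 6.1.1.1 scores a treated subject with no HIV-1 RNA after Day 1 as a responder, with the one possible exception of a Day 1 value of 50 or more followed by withdrawal. So it is too strong to say that such a subject can never fail.

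A reader might also infer that the Part 1 PVR of 100%, or the final PVR, is inflated. The documents do not support that: they give no count of subjects without post-Day 1 results, and the count may be zero. What can be said is conditional. Each such subject is worth 1.6 points at n = 64. If there are no rebounds and they are scored as failures, one or two take the exact lower limit from 94.4% to 91.6% or 89.2%; if they are left out, it is 94.3% or 94.2%. The change is worth making because the bias has one direction, the expected number of failures is very small, and the remedy is short.

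**What to change.** 1. State in SAP 6.1.1.1 that a responder needs at least one post-baseline HIV-1 RNA by the upper limit of the analysis window (Day 98 for Week 12), and whether a Day 1 value can count towards rebound.
2. Count subjects with no such value as non-responders on their own line, in keeping with Missing = Failure.
3. Print beside PVR the number of responders with no HIV-1 RNA inside the window. This must accompany item 1, because a subject with only a Week 4 result would still pass.
4. Do the same at Weeks 24 and 48 (upper limits Days 210 and 378).
5. List the change in SAP 6.3, together with the omitted on-treatment condition, which must be reconciled with Protocol 8.4.1.
6. Report PVR under the current SAP 6.1.1.1 rule as well. The trial is open-label and the Part 1 PVR was already known, so a reader should be able to see that the change was not chosen for its result.

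The cost is a few lines of SAP text, an extra table row with the in-window count, and a PVR that may be slightly lower. If every subject has a post-baseline value by the window's upper limit, this requirement leaves the estimate unchanged and the report shows that each responder was sampled.
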